Community based HIV-testing has been implemented in some countries such as Vietnam (Nguyen et al., 2019), Uganda (Ortblad et al., 2018), Malawi and Zimbabwe (Napierala et al., 2019). Non-governmental organizations in Indonesia had conducted study or pilot project on HIV test in men who have sex with men (MSM) outside health facility (Hidayat et al., 2019). This study was done to find an alternative to facility-based HIV testing, however MoH has been rather conservative in supporting non-health facility-based approach outside of mobile clinic testing which involves trained healthcare professional to perform HIV testing procedure according to the algorithm developed by the government. Mobile clinic testing strategy gave out insufficient result, especially in terms of linking those with positive HIV result for further follow-up and initiation of treatment. Cost-effectiveness of this approach was also doubted, at least in Jakarta (Cantelmo et al., 2019). This study found that the cost needed for mobile testing to identify at least one HIV positive case among FSW was almost six-times fold higher compared to finding similar target among transgender and MSM, and seventeen-times fold higher than those for identifying one HIV positive case among people who inject drugs (PWID). For the effective use of resource, this study suggested modification of the test frequency, time, and location for FSWs in Jakarta. In addition, this study also recommended the need for alternative strategies to increase HIV test uptake among FSW.

FSWs community are at greater risk of not only HIV infection, but also stigma, discrimination and violence. They first face stigma and discrimination due to engaging in sex work itself, or from HIV stigma, particularly in contexts of HIV burden, which later affect their access to HIV testing (UNAIDS, 2016). The latest WHO guidelines have highlighted HIV self-testing (HIVST) as important tool to identify more people with undiagnosed HIV and at high risk of HIV infection. Protection of privacy and confidentiality is one of the advantages of this modality which allows for removing stigma as barriers to access services. HIVST has been shown to be acceptable across varieties of population globally including for FSWs community (King et al, 2013). Oral fluid HIVST is an alternative to traditional HIV testing services in the facility or other healthcare provider testing (UNAIDS, 2016).

3. HIV Self-testing Using Oral Fluid Test

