- f. For clients with reactive community screening results, (i) advise them (online) to get a confirmatory test at selected health facility (ii) offer to facilitate making an appointment for testing to accompany them to a health facility for testing, and (iii) provide FSW with a referral card to be submitted to the health facility. Another possible option is to have the referral cards within the test kit, therefore when FSW with reactive results do not wish for their result to be revealed other than towards the post-test survey platform and health officers, they can access health facility for confirmatory test. Information on what's needed to be done when one finds reactive test result has to be mentioned in detail within the instructional fliers or video.
- g. For clients with non-reactive community screening results, (i) again online reinforce prevention measures, (ii) remind them of the need for periodic testing and (iii) offer a referral card in case FSW want a confirmatory test at a health facility (if there is concern about the accuracy of the community screening test). In the case where referral card is included within every box containing test kit, FSW with non-reactive result might still be able to bring the card to selected health facility to get a confirmatory test.

4. Implementation Guidelines for Control Group (Standard Program)

For the control group, there will be no new interventions implemented (that is, they will continue with “business as usual”). In each control site, there is an implementing unit (IU) responsible for conducting outreach for FSWs. The outreach target is set up for one year, meaning that a sex worker will only be outreached once in a year. The outreach packet should include condoms and lubricant distribution as well as HIV-AIDS education media distribution. Furthermore, each IU also has a certain number of HIV tests to fulfill every six months. To achieve the target, the IU should reassure sex workers to do HIV test at least once every six months. While it is possible for a sex worker to have HIV test in three months interval, only one test is count for a sex worker every six months. The test could be conducted at health facilities or mobile clinics. A mobile clinic could be conducted at any place where convenient to the participants, such as workplace or living space. For FSWs with reactive test results, they will then be referred to health facility to start on ART.

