Except for outreach, all above mentioned activities are incentivized. Below are details of incentives given to PL/PE based on current standard program:

1. Cash incentive of 70,000 IDR for every client who referred for HIV testing to health facilities.
2. Cash incentive of 25,000 IDR for every client taking the test after being reached through mobile outreach.
3. Cash incentive of 50,000 IDR for every client with positive confirmatory test starting on ART.

5. Incentives for Participation

Incentives will be given for different participation role in this study:

1. For all eligible FSWs participating in baseline survey will be given 50,000 IDR
2. For FSWs taking VCT and reporting the results will be given 100,000 IDR
3. For FSWs doing CBS AND uploading/sending test result will be given 100,000 IDR
4. For FSWs participating in post-test survey (both assisted and unassisted) will be given 50,000 IDR
5. Cash incentive 100,000 IDR for transportation and registration and/or fee for confirmatory test for CBS **reactive result** for FSWs who go to health care facility for confirmatory test (assisted and unassisted)
6. Cash incentive 100,000 IDR for transportation and registration and/or fee for confirmatory test for CBS **non-reactive result** for FSWs who go to health care facility for confirmatory test (assisted and unassisted)

Incentives will be given for different role of PL/PE in this study:

1. For PL/PE who assists FSWs for taking self-screening (including filling in baseline and post-test) will be given 150,000 IDR
2. For PL/PE who delivers test kit to FSWs who opt for unassisted screening AND obtain baseline survey on the spot will be given 100,000 IDR

Incentives will be given for health facility:

For collecting data on FSWs who do confirmatory test (assisted and unassisted). Funds to cover additional operational cost will be given to each implementing unit (IU) for delivering test kit via Go-Pay/Grab Pay Top-Up to client's address.

D. LINKAGE TO HEALTH SERVICES FOR ARV INITIATION

Outreach workers will navigate clients to health care facilities for confirmatory test and ARV initiation if the result is confirmed as positive. Health care facilities in each district will be selected by their readiness to offer Test & Treat (T&T). Clients who come for confirmatory test are expected to be started for ARV initiation on the same day of confirmatory test.

E. DATA COLLECTION PROTOCOLS

1. Baseline survey

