- How likely is it that the client will get a HIV test at a health facility as a result of the community screening test, on a scale of 1-5
- Comments and suggestions.

3. Routine Recording

Because of limitations in the data recorded and reported by health facilities, the study will rely primarily upon data recorded by IU outreach staff. Modifications will be made to the data recording and reporting systems currently being used to facilitate collection of the data needed for the study in a manner that minimizes additional recording and reporting burden. The nature of the adjustments to be made will be different for "assisted" and "unassisted" community screening.

To capture the data needed for of this study, the following data need to be recorded:

No	Data Recorded	Intervention Group	Control Group
1	Number of FSW contacted via outreach that were at least 6 months since their last HIV test for whom testing at a health facility was recommended	Yes	Yes
2	Numbers of FSW offered for HIV test at health facility	Yes	Yes
3	Numbers agreeing and disagreeing to testing at a health facility	Yes	Yes
4	Of those agreeing to getting tested at a health facility, the numbers that actually went to a health facility and were tested for HIV	Yes	Yes
5	Number of FSW offered for OFT screening	Yes	No
6	Among FSW not agreeing to be tested at a health facility, the numbers that agreed to (1) assisted community HIV screening and (2) unassisted community HIV screening	Yes	No
7	Numbers that were actually screened, assisted and unassisted	Yes	No
8	The number of community screening tests that were reactive	Yes	No
9	Among FSW with reactive community screening tests, the numbers that were subsequently tested at a health facility	Yes	No
10	Number of FSW initiating ART	Yes	Yes

For **unassisted** approach, additional information will be gathered as indicated below:

1. Numbers of FSW who access the link online
2. Numbers of FSW who are deemed eligible
3. Numbers of FSW who fill in baseline survey and agree to participate
4. Numbers of FSW who agree to take HIV test at health facility
5. Numbers of FSW who request the kit being delivered vs picking-up at fixed location
6. Numbers of FSW who upload the test result
7. Numbers of reactive vs non-reactive test result
8. Numbers of FSW who complete the post-test survey

9. Among FSW with community screening tests, the numbers that were subsequently tested at a health facility (reactive OR non-reactive)
10. Number of FSW initiating ART

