In the event that participants' data are collected by paper, a procedure to upload the data into the established online system will be developed. Each data manager in the IUs needs to conduct the procedure regularly. This is to ensure that all data are being captured thoroughly.

F. DATA ANALYSES

The data analyses to be undertaken will be directed to addressing the research questions laid out at the beginning of the protocol and statistical tests appropriate to each specific analysis will be performed to inform the interpretation of results. The specific steps in the data analysis will be as follows:

1. Compare the characteristics of FSWs who receive self-testing and blood testing.

2. Compare the characteristics of FSWs who receive assisted and unassisted self-testing.
3. Compare proportion of FSWs taking confirmatory test out of those who receive the test in the assisted and unassisted self-testing.
4. Compare the proportion of FSWs who receive HIV test out of those who got offered for the test (including self-testing) in the intervention group with proportion of FSWs who receive HIV test in the control group.
5. Compare the proportion of FSWs taking confirmatory test (including self-testing) out of those receive the test in intervention groups and control group.
6. Compare the proportion of HIV positive in the assisted, unassisted (intervention) and HIV positive in the control group.
7. Compare the proportion of ART initiation in the assisted, unassisted (intervention) and the control group.
8. Calculate the cascade of HIV testing and treatment.
9. Compare stigma scores and FSWs who went to a health facility for HIV testing between assisted, unassisted group.
10. Compare the HIV and STI risk behaviors between assisted and unassisted group.

G. CONTINGENCY STUDY DESIGN

Should the OraQuick® test kits not become available in sufficient time to conduct a full-scale cRCT, a smaller-scale study will instead be undertaken. The purpose of the smaller study is the same as the cRCT described above, and the same protocol described above will be implemented. But the comparison is achieved targets between before and after intervention – there will be no comparison districts. The study will be undertaken in three (3) districts. The three districts will be selected from different parts of Indonesia, and they are: Kota Bandung (west part of Indonesia), Kota Denpasar (central part of Indonesia), and Kota Makassar (center-east part of Indonesia).

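### Mobile-clinic blood tests are part of standard care but have no row in the study's data list, so analysis 4 can understate testing in the comparison arm and overstate the gain

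*Combined protocol and SAP*

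**What the plan says.** Section C.4 describes the comparison arm as the standard programme. On venue it says "The test could be conducted at health facilities or mobile clinics", and then "A mobile clinic could be conducted at any place where convenient to the participants, such as workplace or living space". The outreach incentives in the same section price the venues separately. A referral to a health facility earns 70,000 IDR, and for mobile testing the entry is "Cash incentive of 25,000 IDR for every client taking the test after being reached through mobile outreach". Section A.2 also treats mobile clinics as something other than facility testing: it describes the ministry as cautious about any "non-health facility-based approach outside of mobile clinic testing".

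Section E.3 says that "the study will rely primarily upon data recorded by IU outreach staff" and then lists the data the study needs. Row 4, required in both arms, is the only row for completed blood tests among women offered facility testing: "Of those agreeing to getting tested at a health facility, the numbers that actually went to a health facility and were tested for HIV". Row 7, required in the intervention arm only, is "Numbers that were actually screened, assisted and unassisted". No row covers a blood test at a mobile clinic.

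Section F, item 4, reads "Compare the proportion of FSWs who receive HIV test out of those who got offered for the test (including self-testing) in the intervention group" and sets this against the proportion of control women who receive an HIV test. It does not define venue on the control side. Objective 1 (Section A.6) concerns knowledge of HIV status. Objectives 2 and 3, and the sample size in Section B.5, concern testing at health facilities.

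**The concern.** A woman in a comparison district who will not visit a facility can still have a formal blood test at her workplace or home. She then knows her status, but the listed data have no place for that test. A woman in an intervention district who declines a facility and tests herself at the same kind of place is counted. Off-site testing therefore enters one arm of analysis 4 and not the other.

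At stake are the headline comparison of testing uptake and the answer to objective 1. Part of a reported gain could be testing that the comparison arm also delivered but the study did not record. The plan as written would give no means of detecting this afterwards.

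**Working it through.** **Inputs.** From Section B.5: comparison proportion 0.5, intervention proportion 0.6, target difference 10 points, design effect 1.5, 635 women per group (761 with the 20% allowance). The share s of blood tests done at mobile clinics is not in the documents. It is an assumption here, shown over a range.

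**The plan's own figure.** Take n = [Zα√(2P(1−P)) + Zβ√(P1(1−P1)+P2(1−P2))]² / (P1−P2)², with P = 0.55, Zβ = 1.282 and one-sided Zα = 1.645. This gives 422.03, rounded up to 423. Then 423 × 1.5 = 634.5, so 635, and 634.5 × 1.2 = 761.4, so 761. Both printed figures reproduce. (The printed Z of 1.96 would give 519 × 1.5 = 778.5; that is a separate matter.) The effective size per group used below is 635 / 1.5 = 423.

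**Analysis 4.** Let Mc and Mi be the proportions of offered women whose only test was at a mobile clinic, in the comparison and intervention arms. Each arm's recorded proportion falls short of the truth by its own M, so the error in the difference (intervention minus comparison) is Mc − Mi. Set the true any-test proportion at 50% in both arms, so that there is no real effect.

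- Scenario A: every intervention test is recorded (Mi = 0). The recorded comparison proportion is 0.5(1−s) and the false difference is 0.5s.
- Scenario B: the same share s of blood tests is missed in both arms, and 20 of the 50 intervention points are self-tests. The recorded intervention proportion is 0.30(1−s) + 0.20 and the false difference is 0.5s − 0.3s = 0.2s.

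| s (assumed) | Comparison, recorded | A: false difference | B: intervention, recorded | B: false difference |
|---|---|---|---|---|
| 5% | 47.5% | 2.5 points | 48.5% | 1 point |
| 10% | 45% | 5 points | 47% | 2 points |
| 20% | 40% | 10 points | 44% | 4 points |
| 40% | 30% | 20 points | 38% | 8 points |

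Under scenario A, with 423 effective women per group, a true null would be declared significant with probability 0.31 (two-sided 5%) or 0.43 (one-sided 5%) at s = 10%, and 0.83 or 0.90 at s = 20%. If no self-tests replace blood tests and omission is equal, the false difference in analysis 4 is zero.

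**Facility testing only.** Row 4 leaves out mobile tests in both arms, so the arithmetic differs.

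- Equal omission with a true 60% v 50%: the recorded difference is 0.1(1−s). It is 54% v 45% (9 points) at s = 10% and 48% v 40% (8 points) at s = 20%. The effect is diluted.
- Full displacement of mobile testing to self-screening, with 50% blood-tested in the comparison arm and s = 20%: the comparison arm has 40% at facilities and 10% mobile, the intervention arm 40% at facilities and 10% self-screened. The recorded comparison is 40% v 40%, a difference of zero, while formal blood testing is 40% v 50%. A loss of 10 points is hidden.
- The same case, with all of the displaced 10% then confirming at a facility and being counted: the record shows 50% v 40%, although formal testing is 50% in both arms. Here the gain is only a change of venue. These women declined a facility at first, so their tests fall under row 9 or item 9 of the unassisted list, not row 4.

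**The case against.** Several points on the other side stand. Row 4 applies to both arms, and Section C.1 adds self-screening to the existing package, so mobile tests may be missed in intervention districts too. A reader might infer that the facility-testing effect is inflated by 5-10 points. The documents do not support that: equal omission dilutes that effect, and displacement alone produces no recorded gain.

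A reader might also take row 4 to be the source of the primary outcome and conclude that this outcome should be replaced by any blood test. Section A.6 lists five primary questions, and Section E.3 labels no row as primary. Objectives 2 and 3 and the sample size explicitly concern health facilities. Section A.2 reports weak linkage after mobile testing, so a facility outcome is a defensible choice.

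The incentives do not settle how much mobile testing would be displaced. Outreach staff earn 100,000-150,000 IDR for self-screening against 25,000 IDR for a mobile test, but the standard programme already pays 70,000 IDR for a facility referral.

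Nor do the Table 4 counts create a baseline mismatch in the randomized design. They form the randomization strata (Section B.4), and no analysis in Section F uses them as a baseline outcome.

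Finally, the control side of analysis 4 does not restrict venue, so mobile tests are undefined there, not excluded. Implementing units probably hold the counts, because they work to six-monthly testing targets and the mobile test carries an incentive. Section C.2(g) leaves current tracking unchanged. This makes the gap easy to close, but the plan does not say that those counts will be used, and its list of needed data omits them.

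**Conclusion.** The gap is real and should be closed. Standard care provides formal tests at two venues, the data list captures one of them, and off-site self-tests are captured in the intervention arm only. If analysis 4 and objective 1 are answered from the listed data, comparison women tested at mobile clinics count as untested, and the gain can be overstated.

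The size depends on a mobile share that the documents do not give. With 50% truly tested in both arms, a share of 10-20% gives 5-10 false points if all intervention tests are recorded, the upper end equalling the whole design difference. It gives 2-4 points if mobile tests are missed equally and 20 of the 50 intervention points are self-tests. These figures are illustrations of analysis 4, not estimates for this trial.

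For facility testing the direction is open. The effect can be diluted, a loss of formal testing can be hidden, or a change of venue can look like a gain if displaced women go on to confirm at a facility.

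**What to change.** - Add a row to the Section E.3 list, in both arms, for women blood-tested at a mobile clinic, with all women offered testing (row 2) as the denominator.
- In analysis 4 and for objective 1, count any HIV test at any venue in both arms: facility plus mobile, plus self-test in the intervention arm. State this definition in Section F.
- Keep facility testing as the stated outcome for objectives 2 and 3. Include facility tests made after screening (row 9, which as listed covers reactive screens only, and item 9 of the unassisted list).
- Report facility plus mobile blood testing beside the facility outcome as a sensitivity analysis, so that a real gain can be told from a change of venue.

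The cost is one extra count on an existing form and a few lines of definition. The apparent effect may be smaller if mobile testing is common in comparison districts.

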The study will produce scientifically strong evidence as to whether two alternative models of community HIV screening among FSW (assisted and unassisted) result in (1) increased rates of formal HIV testing at health facilities and (2) increased rates of treatment initiation in districts in which the community screening intervention is added to the existing FSW community outreach model.

Two alternative study protocols are described in this document. The bulk of this document presents a protocol for a community randomized controlled trial (cRCT), which is the preferred research design option. However, due to a delay in procurement of the OraQuick® rapid HIV test kits that are to be used in the study, there may be insufficient time to undertake a full cRCT.¹ Accordingly, a contingency protocol that can be implemented in a shorter period of time is also presented.

6. Study Objectives

The primary objectives of this study will provide answers to the following five (5) questions:

1. Does the proportion of FSW who know their HIV status increased?

¹ All research activities must be completed by 31 December 2020.

2. Does the introduction of community HIV screening among FSW increase the rate of HIV testing at health facilities?
3. Does “assisted” or “unassisted” community HIV screening among FSW result in a larger increase in the rate of HIV testing at health facilities?
4. Does “assisted” and “unassisted” community HIV screening among FSW results in a larger increase in the rate of HIV positive case finding?
5. Does the introduction of community HIV screening among FSW increase the rate of initiation of ART?

The secondary objectives of this study will provide answers to the following two (2) questions:

1. What is the acceptability of community-based self-screening for FSWs participating in this study?
2. What is the satisfaction of FSWs participating in this study towards delivery of community-based self-screening?

B. STUDY DESIGN

1. Design Summary

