Participants with reactive or indeterminate result resulting from either assisted or unassisted methods will be encouraged to get a confirmatory test at a health facility. A confirmatory test will also be suggested for participants with non-reactive result. The difference between these two result groups will be the level of encouragement given to do the confirmatory test. While participant with reactive or indeterminate results will be strongly encouraged, participants with a non-reactive result will be suggested for a confirmatory test. These suggestions are derived from Indonesia's current guideline on HIV detection, where the confirmatory test is to be done at the health facility using the HIV blood test.

Figure 1. Study Flowchart

[figure not shown]

Table 3. Global Fund HIV testing targets in 23 districts for 2019-2020

No	Province	Districts	Region	Target of HIV Testing			
				P3	P4	P5	P6
1	Sumatera Utara	Kota Medan	1	904	904	1,002	1,002
2	Sumatera Utara	Kab. Deli Serdang	1	406	406	450	450
3	Sumatera Selatan	Kota Palembang	1	1,371	1,371	1,520	1,520
4	Lampung	Kota Bandar Lampung	1	393	393	435	435
5	Banten	Kota Tangerang Selatan	1	223	223	247	247
6	Banten	Kab. Tangerang	1	820	820	909	909
7	DKI Jakarta	Kota Jakarta Selatan	1	536	536	594	594
8	DKI Jakarta	Kota Jakarta Timur	1	877	877	973	973
9	DKI Jakarta	Kota Jakarta Pusat	1	1,341	1,341	1,486	1,486
10	DKI Jakarta	Kota Jakarta Barat	1	1,318	1,318	1,461	1,461
11	DKI Jakarta	Kota Jakarta Utara	1	1,431	1,431	1,586	1,586
12	Jawa Barat	Kota Bogor	2	474	474	525	525
13	Jawa Barat	Kota Bekasi	2	248	248	275	275
14	Jawa Barat	Kota Bandung	2	582	582	645	645
15	Jawa Barat	Kota Depok	2	374	374	415	415
16	Jawa Tengah	Kota Semarang	2	510	510	565	565
17	Jawa Tengah	Kota Surakarta	2	172	172	190	190
18	Jawa Timur	Kota Malang	3	84	84	93	93
19	Jawa Timur	Kota Surabaya	3	1,173	1,173	1,300	1,300
20	Bali	Kota Denpasar	3	1,407	1,407	1,559	1,559
21	Sulawesi Selatan	Kota Makassar	3	1,444	1,444	1,600	1,601
22	Papua Barat	Kota Sorong	4	438	438	485	485
23	Papua	Kota Jayapura	4	786	786	871	871

Table 4. Achieved target of HIV testing per semester in 23 priority districts (2018-2019)

No	Kab/Kota	Region	Achieved target of HIV testing per semester
1	Kota Denpasar	3	982
2	Kota Makassar	3	866
3	Kota Palembang	1	694
4	Kota Jakarta Utara	1	612
5	Kota Medan	1	575
6	Kota Surabaya	3	568
7	Kota Jakarta Barat	1	544
8	Kota Bandung	2	487
9	Kota Jakarta Timur	1	479
10	Kota Jakarta Pusat	1	473
11	Kota Jakarta Selatan	1	448
12	Kota Sorong	4	415

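### The counts listed in E.3 do not include assisted women's facility tests after a non-reactive screen, so analysis 3 cannot be done on its stated definition for both methods

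*Combined protocol and SAP*

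**What the plan says.** **Data source.** E.3 (Routine Recording) states that "the study will rely primarily upon data recorded by IU outreach staff", because of limits in what health facilities record and report. It then tabulates the data to be captured and adds a second list for the unassisted approach only.

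**Later facility tests.** Three listed items bear on them:
- Table row 9, intervention group: "Among FSW with reactive community screening tests, the numbers that were subsequently tested at a health facility".
- Unassisted list, item 9: "Among FSW with community screening tests, the numbers that were subsequently tested at a health facility (reactive OR non-reactive".
- Table row 4, both groups: "Of those agreeing to getting tested at a health facility, the numbers that actually went to a health facility and were tested for HIV".

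**Analysis.** Section F, item 3: "Compare proportion of FSWs taking confirmatory test out of those who receive the test in the assisted and unassisted self-testing". This bears on primary objective 3, which asks whether assisted or unassisted "community HIV screening among FSW result in a larger increase in the rate of HIV testing at health facilities".

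**Confirmatory tests after non-reactive screens.** B.1 says: "A confirmatory test will also be suggested for participants with non-reactive result". C.2(f) and C.3(g) offer a referral card to these women in the assisted and unassisted methods respectively. C.5 (incentive 6) pays 100,000 IDR to those who attend, in both methods.

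**The concern.** Analysis 3 puts all self-tested women in the denominator. Its numerator is women who took a confirmatory test, and the plan uses that term after non-reactive screens too. The listed counts support this numerator for the unassisted method through item 9. They do not support it for the assisted method, because the only listed count that reaches assisted women's later tests, row 9, stops at reactive screens.

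At stake is the head-to-head comparison of the two methods, for which B.5 asks for 761 women each. With E.3 as it stands, the analyst must answer a narrower question than the one stated or compare proportions whose numerators mean different things.

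**Working it through.** **1. What the listed items identify.** Let R and N be the numbers of women tested at a facility after a reactive and a non-reactive screen, with subscript a for assisted and u for unassisted. Let n be the number screened.
- Analysis 3 needs (R_a + N_a)/n_a against (R_u + N_u)/n_u.
- Row 7 gives n_a and n_u, as it is split by method.
- Row 9 gives R_a + R_u. It is not split by method.
- Unassisted item 9 gives R_u + N_u.
- Row 4 gives none of the four. It covers women who agreed to facility testing, whereas screening is offered to those who declined it (B.1, C.1, C.2(b)).

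N_a appears in no listed item. R_a cannot be obtained by subtraction, because row 9 and item 9 cover different screening results. Neither item mentions indeterminate results, although B.1 sends those women for confirmation and Annex 7 has a code for them.

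**2. What the forms shown add.** Annex 5 records whether a woman went to a facility, but it is for women who chose the blood test. Annex 7 holds kit code, method and screening result, with no field for a later test. Annex 8 (item 11) asks only how much she wants to confirm the result.

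**3. The two ways to proceed from the listed counts.**
- *Reactive women only.* If method is attached through the kit ID, R_a/n_a can be compared with R_u/n_u. The comparison is like for like, but narrower than analysis 3.
- *Row 9 for assisted, item 9 for unassisted.* The numerators are then R_a and R_u + N_u. With equal behaviour in both methods, the assisted proportion falls short by (1 − r) × u, where r is the share of screens that are reactive and u is the facility-test uptake after a non-reactive screen.

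**4. Size of the shortfall under the second route.** Inputs: 3% positivity (B.5, assumed there for facility testing and applied here to screened women); sensitivity 90.14% and specificity 99.13% (A.3).

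r = 0.03 × 0.9014 + 0.97 × (1 − 0.9913) = 0.0355, so 1 − r = 0.9645.

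The documents give no value for u, so it is assumed:

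| Assumed u | Shortfall, 0.9645 × u (points) | Uncounted women per 761 |
|---|---|---|
| 0% | 0 | 0 |
| 1% | 1.0 | 7 |
| 2% | 1.9 | 15 |
| 5% | 4.8 | 37 |
| 10% | 9.6 | 73 |

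For scale, B.5 sizes the study for a 10-point difference. The positivity assumption matters little: at 1% and 10% positivity r is 1.8% and 9.8%, so at u = 10% the shortfall is 9.8 and 9.0 points. If other sources recovered half the missing tests, the shortfall would halve, for example to 2.4 points at u = 5%.

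**5. Size of the narrower route.** At r = 0.0355, the reactive women number about 761 × 0.0355 = 27 per method.

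**The case against.** A reader might infer that the plan builds in a bias against assisted screening. The documents do not support that. Row 9 is not split by method, so the listed tallies contain no assisted numerator that could be biased. No section tells the analyst to use row 9 for one method and item 9 for the other. Once method is linked, row 9 can be applied to both, with item 9 as additional information.

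There is also evidence that the missing counts may be obtainable:
- E.4(a) requires the kit ID on every form linked to results, including each implementing unit's routine record. The Annex 9 referral card carries the kit code.
- C.2(g) keeps the existing tracking of who was tested, whatever the screening result, and has no counterpart in the unassisted section. E.3 says of the recording changes that "The nature of the adjustments to be made will be different for" the two methods. Item 9 may therefore fill a gap that exists only where there is no face-to-face contact.
- C.5 pays facilities to collect data on confirmatory tests in both methods, and the attendance payments leave a trail.
- E.1 expects to know who presented at facilities, and analysis 9 compares facility attendance by method without limiting it to reactive women.
- Annex 1, the recording flowchart, is not shown and may settle the matter. Its absence from the text does not count against the plan.

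Most of this stands, and it removes any claim of an established direction or size of bias. It does not close the gap in the list. None of these sources is named for analysis 3, and E.3 relies on outreach records precisely because facility data are limited. A reason for collecting data differently by method is not a reason for counting different events in a comparison of the methods.

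**Conclusion.** The point holds as a gap in definition and recording. E.3 does not list the assisted count that analysis 3 needs, so from the listed counts the analysis is either limited to reactive women or made with unlike numerators. The shortfall of about 0.96 × u arises only if row 9 is used for assisted and item 9 for unassisted. It rests on an assumed u, on applying B.5's 3% positivity to screened women, and on no recovery from other sources. It is zero if no non-reactive woman goes on to a facility test.

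A reader might also want a probability of a falsely significant result. The documents do not support one. It would need an uptake figure, and B.5's design effect of 1.5 is for clustering by district, whereas these methods are chosen by women within the same districts. That self-selection is a separate limit on the comparison. Confidence is medium, chiefly because Annex 1 could not be read.

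**What to change.** Reword row 9 along these lines: *of the women who had a community screening test, how many later had an HIV test at a health facility, broken down by screening result (reactive, non-reactive, indeterminate) and by method (assisted, unassisted)*. State in section F that analysis 3 uses this one definition for both methods. Add a sentence saying that the count is linked by kit ID to the Annex 7 result form, the referral cards and the health-facility data. If Annex 1 already provides for this, bring row 9 and item 9 into line with it.

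The cost is one reworded row, a line in section F and one linkage sentence, with slightly more recording by outreach staff. The implementing units' recording form and the content of Annex 1 are not shown, so any change to them cannot be sized. The change is best made before data collection. Afterwards, the missing counts depend on what the other sources happen to hold.
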